Potential participants will be identified via screening and then recruited. Screening will involve applying the selection criteria to the Medicaid claims and HIV surveillance data to identify potential participants. We will screen for potential participants given the study's goal is real-time identification of Medicaid members living with HIV and at early risk of falling out of care (as indicated by a late ART prescription refill(s)). Potential participants identified via screening will then be recruited. A simple schematic of screening and recruitment processes for potential participants is shown in **Figure 2**. Screening and recruitment will occur according to existing interagency and contractual agreements, which will collectively authorize Virginia Commonwealth University (VCU) personnel to implement and evaluate the AIMS program for evidence-based quality improvement on behalf of Virginia Medicaid.

Figure 2. Schematic of screening and recruitment for eligible potential participants

Screening will involve: 1) Initial identification of eligible potential participants using the Medicaid claims, and 2) Data integration with HIV surveillance data and confirmation of potential program participant eligibility. Screening activities will occur on a monthly basis during study enrollment, which is anticipated to be 6 months.

Initial eligibility. We will use the Medicaid claims to identify a preliminary sample of eligible potential participants. We will select from the Medicaid claims those enrollees who satisfy inclusion criteria: current enrollment in Virginia Medicaid, continuous Virginia Medicaid enrollment for >9 months, current

age 19–64 years, non-dual eligible for Medicare, identified as living with HIV according to the HIV case identification algorithm (Aim 1), and a late ART prescription refill(s) by >30–365 days in the prescription claims. ‘Late ART prescription refill(s) by >30–365 days’ refers to the most recent ART prescription(s) that is >30–365 days in the prescription claims after the expected date of refill or renewal.

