We will exclude enrollees who have a record of third-party health insurance during the past 3 months. We will exclude enrollees who have a missing phone number and/or mailing address. We will exclude those experiencing within-class ART switches due to medication toxicity (defined as a new within-antiretroviral class ART prescription claim >30 days of the expected date of ART prescription refill or renewal). We will also exclude those enrollees experiencing ART resistance and thus switching to a new regimen (defined as a claim for an antiretroviral drug in a new ART class occurring >30 days of the expected date of ART prescription refill or renewal). We will exclude enrollees whose linked HIV provider is a provider practicing at a facility offering PositiveLinks. The study will exclude enrollees who do not have a record in Virginia’s HIV surveillance data, as a record in the HIV surveillance data confirms HIV status. The study will exclude enrollees who do have a record of an ART prescription(s) in the Virginia HIV surveillance data, but did not have a record of an ART prescription(s) in the claims data, as an additional confirmatory check on study eligibility. We will exclude enrollees who do not speak English, as PositiveLinks has not been validated in languages other than English.

An initial database of eligible potential participants will be constructed and include: first and last name, social security number, complete or partial address, race/ethnicity, sex at birth, and date of birth; and expected date of ART prescription fill, refill, or renewal; and an indicator for a late ART prescription refill(s) by >30–365 days). Analysis will be conducted by authorized VCU personnel and saved on the Virginia Medicaid servers per an amendment to an existing Interagency Agreement between Virginia Medicaid and VCU.

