Confirmed eligibility. The initial database of eligible potential participants will be integrated with an extract of HIV surveillance data from the Virginia Department of Health. The integrated data will be used to confirm HIV status of eligible potential participants, their current/prior ART prescription(s) from state health department program databases, and potential participant eligibility for the study. Authorized Virginia Medicaid personnel will securely transfer the initial database of eligible potential participants to the Virginia Department of Health per an existing Interagency Agreement. Data integration and potential program participant eligibility will occur on a monthly basis during the enrollment period. After data transfer, authorized VCU personnel will use deterministic and probabilistic methods to link the two databases using the following variables: first and last name, social security number, complete or partial address, race/ethnicity, sex at birth, and date of birth. We note that complete information about current or prior ART prescriptions, which we are using to confirm potential participant eligibility where possible, is not available for all Virginians living with HIV; this is because only some Virginians have accessed state programs providing antiretroviral prescriptions. Given Medicaid’s comprehensive ART prescription coverage, we anticipate that Virginia Department of Health databases with ART prescription will be used primarily to ascertain if a potential participant has previously received ART prescriptions.

Recruitment

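### The check against state ART records cannot exclude anyone who met the inclusion rule, so people already on state-supplied treatment can remain among the never-contacted controls

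*Combined protocol and SAP*

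**What the plan says.** **Inclusion (Screening, Initial eligibility).** A person must have "a late ART prescription refill(s) by >30–365 days in the prescription claims". The definition that follows says the term "refers to the most recent ART prescription(s) that is >30–365 days in the prescription claims after the expected date of refill or renewal". Lateness is therefore measured in Medicaid claims alone, from an ART prescription that appears there.

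**Exclusion (same section).** "The study will exclude enrollees who do have a record of an ART prescription(s) in the Virginia HIV surveillance data", and the sentence continues "but did not have a record of an ART prescription(s) in the claims data, as an additional confirmatory check on study eligibility". Neither half carries a date window.

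**Linkage (Screening, Confirmed eligibility).** Each month the linked data are to confirm HIV status, "their current/prior ART prescription(s) from state health department program databases, and potential participant eligibility for the study". The section concedes that ART information is incomplete, since "only some Virginians have accessed state programs providing antiretroviral prescriptions". Citing Medicaid's broad ART coverage, it expects that the state ART data "will be used primarily to ascertain if a potential participant has previously received ART prescriptions".

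**Check by contact (Other data and analyses).** Among the data gathered in dealings with participants is ART use at that time, collected to settle eligibility by confirming that no refill has taken place.

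**Controls (Procedures: Usual care arm).** Screening is as for the program arm. There is no recruitment, consent or contact, and only existing secondary data are used.

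**The concern.** The person an outside-source check needs to catch is one whose Medicaid fills stopped but who now receives ART through a state program. In claims that person looks late, but is in fact on treatment and probably suppressed. The exclusion appears to be aimed at this case, yet its second condition (no ART record in claims) is one that no included person can meet.

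The arms then differ in what else can catch such people. Someone recruited to the program arm is asked about current ART use before eligibility is final. A control is not asked anything. If falsely late people are screened out of one arm and kept in the other, the control group contains a subgroup with a better expected outcome that has no counterpart among participants. The propensity model lists patient, provider, hospital and geographical characteristics. Its list is open-ended, but it does not name state-supplied ART, so matching cannot be relied on to remove the difference.

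The primary outcome, viral suppression, is affected directly. Adherence is defined from prescription claims, so a control treated through a state program would probably be counted as non-adherent while on treatment.

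**Working it through.** **1. The two rules side by side.**

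- Inclusion: the most recent ART prescription in claims is more than 30 and up to 365 days overdue. This implies that at least one ART claim exists.
- Exclusion: an ART record in state data *and* no ART record in claims. This requires that no ART claim exists.
- Overlap, taking the text literally: none. The exclusion removes nobody whom inclusion has not already removed.

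**2. Other rules that might catch a state-supplied person.**

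| Step | Program arm | Usual care arm |
|---|---|---|
| Exclusion on state ART records | no effect as worded | no effect as worded |
| Confirmed eligibility, current/prior state ART | intent stated, no decision rule | intent stated, no decision rule |
| Current ART use asked by contact | can remove the person | not possible, no contact |

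Only the last row separates the arms, and it works in one direction.

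**3. Size, as an illustration.** The plan gives no figure for this point, so there is none to reproduce. The inputs are:

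- control suppression among genuinely late people, p_C = 0.50 (the control rate assumed in the sample size section);
- difference 0.28 with 100 per arm (same section), so a program rate of 0.78;
- f, the share of controls who are falsely late: 0.05, 0.10, 0.20 (assumed);
- s, suppression among them: 0.70 to 0.90 (assumed);
- two-sided alpha 0.05 (assumed, as the document states none).

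The contact check is taken to remove all such people from the program arm, which is the extreme case.

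Observed control rate = p_C(1 − f) + s·f. The shift is f(s − p_C), and it does not depend on the true program effect.

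| f | Control rate (s = 0.70 to 0.90) | Bias against program | Observed difference if truly 0.28 |
|---|---|---|---|
| 0.05 | 0.51 to 0.52 | 1 to 2 points | 0.27 to 0.26 |
| 0.10 | 0.52 to 0.54 | 2 to 4 points | 0.26 to 0.24 |
| 0.20 | 0.54 to 0.58 | 4 to 8 points | 0.24 to 0.20 |

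Example: f = 0.20 and s = 0.90 give 0.50 × 0.80 + 0.90 × 0.20 = 0.58, a shift of 0.08.

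**4. Effect on power.** Power = Φ[(d − 1.96·SE0)/SE1], where SE0 uses the pooled proportion and SE1 the separate ones.

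- 0.50 vs 0.78, n = 100 each: SE0 = √(0.64 × 0.36 × 0.02) = 0.0679 and SE1 = √[(0.25 + 0.1716)/100] = 0.0649. Power = Φ(2.26) = 98.8%, consistent with the plan's statement of more than 80%.
- 0.58 vs 0.78: SE0 = 0.0660, SE1 = 0.0644, power = Φ(1.10) = 86.4%.
- 0.54 vs 0.78: power 95.3%.

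At f = 0.20, power therefore falls from 98.8% to between 86% and 95%.

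**5. If the contact check is imperfect.** With a residual share g of falsely late people in the program arm and no true effect, the bias is (g − f)(s − 0.50). It disappears only when g = f, and the step 3 figures are its value at g = 0.

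**The case against.** **The exclusion may have an implied window.** If having no record in claims means none during the late period, the rule catches exactly the right people. This reading is plausible, because the sentence describes itself as a confirmatory check. But the text gives no window, and two programmers could code it differently. The ambiguity stands and itself calls for a dated rule.

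**Confirmed eligibility is a separate step covering both arms.** It states an intent to use current as well as prior state ART data. This is a fair point, and in practice the team may act on a current fill. What is missing is a rule for doing so, and the stated expectation is that the data will show mainly past receipt.

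**The group may be small.** Eligibility requires current Medicaid enrollment and more than 9 months of continuous enrollment, and Medicaid covers ART comprehensively. This stands. No share is given anywhere in the document.

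**A stronger reading.** A reader might infer that state-supplied people stay in both arms and dilute the effect equally. The document does not support that: the section on other data provides for a check of current ART use before a participant's eligibility is final. That check is presumably by self-report and may miss some, but it means retention in the program arm cannot be taken as given.

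**The state data may lack dates or days' supply.** The document does not list these fields. The fix has to allow for their absence.

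**Conclusion.** The concern holds as a flaw in the written rule with a one-sided consequence. Taken literally, the exclusion removes nobody, and no other written rule lets a current state-supplied fill overturn late status. Contact can correct this for participants but not for controls, so any bias in viral suppression would tend to run against the program.

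The logical part needs no assumption beyond the literal reading. The size rests entirely on assumptions: with 5–20% of controls falsely late and 70–90% of them suppressed, about 1–8 points, taking the contact check as fully effective. At the planned difference of 0.28 the study would keep good power even at the upper end. The same shift would matter more if the true effect were smaller, since its size does not shrink with the effect. The document does not support a claim that the bias is known to be material. The change is worth making because the flaw is plain in the text and the linkage needed to repair it is already planned.

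**What to change.** Replace the exclusion with one dated rule, applied identically to both arms at the monthly linkage. Suggested wording:

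> Exclude enrollees whose state health department records show an ART fill after the last Medicaid ART claim, such that they are not more than 30 days late on the date late-refill status is confirmed. Where days' supply is not recorded, the fill date alone is used, by a convention fixed before linkage.

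The date on which late status is confirmed already starts follow-up for controls, and the monthly screening can supply it for the program arm, so no new index date is needed. Reconcile Initial eligibility, Confirmed eligibility, Procedures: Usual care arm, and Other data and analyses with this rule.

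Report by arm how many people the rule removes, and how many participants are removed only by the contact check. The second count indicates how much asymmetry is left.

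Cost: one rule and a date comparison within an existing linkage, provided the state extract holds fill dates, which the team should confirm. Slightly fewer people will be eligible. People without state program records remain unchecked, a limit the protocol already concedes.

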Recruitment activities for eligible potential participants will involve: 1) a mailed introductory letter to eligible potential participants, 2) follow-up phone calls and text messaging about the study, and 3) certified letters (on request). For each monthly screening of potential participants, recruitment activities will occur over approximately a two-week period. Contact information for eligible potential participants will be available in the Medicaid claims data. We emphasize that recruitment activities are designed to maintain participant privacy and confidentiality regarding HIV status (e.g., the printed introductory letter will not make specific mention of HIV). National data suggest that nearly 4 of 5 people living with HIV report feelings of any HIV-related stigma, with approximately 60% indicating that they hide their status from others and 2/3's noting that it is difficult to disclose their status (Baugher *AIDS Behavior* 2017). A recent systematic review indicates that about one-fifth of US adults living with HIV do not disclose their status to anyone, with higher rates of non-disclosure to sexual partners, family, and friends (Obermeyer *Am J Publ Health* 2011). A vast literature documents the negative consequences—including discrimination, violence, and rejection from friends, family, and employers—due to stigma and unintentional disclosure of HIV status (Obermeyer *Am J Publ Health* 2011).

We emphasize that recruitment occurs only for participants in the Program arm. Recruitment does not apply to the Usual Care arm.

Mailed introductory letter. Linkage coordinators will mail eligible potential participants a hard copy letter that introduces the study. The letter will include safeguards—including a general description about the nature of the study and general evaluation team contact information—to protect confidentiality and minimize the risk of HIV status disclosure. For example, the letter will state that the program is about adherence to prescribed medication, versus adherence to prescribed *HIV* medication. The introductory letter will include limited personal information or study-specific contact information in order to maintain confidentiality. However, the letter will include a unique ID to use during identity verification that will occur in follow-up phone conversation(s) (see below).

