Certified letter. The linkage coordinator will offer to mail a certified letter about the study to eligible potential participants who are successfully contacted but do not verify their identity. The letter is intended to legitimize the study and personalize contact with the potential participant. The certified letter will be similar to the mailed introductory letter, although it will have the option to include some tailored language referencing a prior conversation between the eligible potential participant and the linkage coordinator. The letter will include safeguards—including a general description about the nature of the study and general study team contact information—to protect confidentiality and minimize the risk of HIV status disclosure. Eligible potential participants who are sent a certified letter will be re-contacted by the linkage coordinator according to procedures described above.

Procedures: Usual care arm

The Usual Care arm will involve an artificial control sample created through propensity score matching. No contact will occur with these individuals and they will receive no study-specific intervention, consistent with state-level care for late ART prescription refill(s) for Virginia Medicaid enrollees living with HIV in Virginia. Detail for other processes and procedures for this arm are below.

Screening. Screening for controls will occur over the month enrollment period and as described above.

Recruitment. Recruitment of eligible potential participants in the control (Usual Care arm) does not apply. No contact will occur with these individuals.

Informed consent. Informed consent procedures do not apply. Only existing, secondary health information will be used. This health information will be de-identified, with no code key available; consent and HIPAA authorization do not apply.

Follow-up. A 3-month follow-up period will begin on the first date an eligible control is confirmed as having a late ART prescription refill(s) by >30–365 days.

Procedures: Program arm

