inclusion and Virginia Medicaid–Virginia Department of Health matching protocols, we note that no missing data are allowed.

Other data and analyses

Other data to be collected through interactions with participants include the quality improvement initiative's process data. These data will be used to track study progress and facilitate recruitment and enrollment (e.g., number and timing of contact attempts, mailing address for optional certified letter), current ART use to determine final eligibility (i.e., confirmation that the participant has not refilled their ART prescription), and barriers discussed and referrals made.

Additionally, PositiveLinks app metadata and usage data will be collected through the PositiveLinks app. App metadata include: number of app launches, number of app log ins, response rates for daily queries about medication, response rates for daily queries about mood, response rates for daily queries about stress, response rates for weekly quizzes, number of posts to community message board, number of direct messages to linkage coordinator, and number of times visiting resources section. The text of community board posts will also be collected.

Descriptive statistics will be used to summarize recruitment and enrollment, barriers endorsed, referrals made, and PositiveLinks app usage. We may examine correlates of these variables and/or consider these variables as confounders in the primary evaluation analyses. Community board posts from the PositiveLinks app will be examined using textual analysis methods.

Data management

Data management and statistical analysis will be performed using Terradata 16.10, REDCap 10.9.4, and SAS® Software version 9.4 (or most recent VCU- and agency-approved software releases available). Statistical analysis will occur at Virginia Medicaid, Virginia Department of Health, VCU, University of Virginia, and CDC. Intermediate datasets will be stored on Virginia Medicaid servers, Virginia Department of Health servers, and University of Virginia servers. Final limited and de-identified datasets will be stored at Virginia Medicaid, as well as Virginia Department of Health, and also securely transferred to VCU and CDC.

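### The final check that ART has not yet been refilled can be made only in the Program arm, so controls may include people whom the same check would have removed

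*Combined protocol and SAP*

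**What the plan says.** All references are to the combined protocol and SAP.

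- **Screening** is data-based: "Screening will involve applying the selection criteria to the Medicaid claims and HIV surveillance data". The exclusions under Initial eligibility include "We will exclude enrollees who do not speak English", with no data source named for language.
- **Procedures: Usual care arm** uses the same screening: "Screening for controls will occur over the month enrollment period and as described above". It also states: "No contact will occur with these individuals and they will receive no study-specific intervention". Control follow-up of 3 months starts on the first date on which the late refill is confirmed. Control data are de-identified and no code key is kept.
- **Recruitment**: "We emphasize that recruitment occurs only for participants in the Program arm". Each monthly screen is followed by about two weeks of letters, texts and calls, with up to 6 calls per person across all eligible months.
- **Other data and analyses**: "Other data to be collected through interactions with participants include the quality improvement initiative's process data". Among the uses listed for these data is "current ART use to determine final eligibility (i.e., confirmation that the participant has not refilled their ART prescription".
- **Procedures: Program arm**, Table 1: follow-up starts at the final consultation, or for those who receive both phases at the later of the final Phase 2 consultation and joining PositiveLinks.
- **Statistical analysis**: the propensity model considers patient, provider, hospital and geographical characteristics. Refill status at contact is not among those named.

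**The concern.** A Program participant must pass two tests: flagged late in the data, and still unfilled when reached. A control must pass only the first. The second test is closely tied to the outcomes, because having already refilled is nearly the definition of reinitiation and bears on adherence and suppression.

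People can fail the second test in two ways. Some refill on their own between the monthly screen and the call; this happens even if claims are perfect. Others had filled before screening, but the fill was not yet in the claims or was made outside Medicaid. In either case a Program candidate is removed, while a comparable control may stay and be counted as a success.

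Propensity matching on the named covariates cannot correct this, because the result of the check does not exist for controls. The likely consequence is a control arm that looks too good and a program effect that looks too small.

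**Working it through.** **Setting the rules side by side**

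| Step | Program arm | Usual care arm |
|---|---|---|
| Claims and surveillance screen | Yes | Yes |
| Not refilled, confirmed at contact | Yes | Not possible |
| Start of follow-up | Final consultation or joining PositiveLinks (Table 1) | First confirmed-late date |

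The interval between screen and contact is at least part of a two-week recruitment round and can run over more than one month. A fill in that interval disqualifies a Program candidate. In a control it falls after the start of follow-up and counts.

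**The plan's own figure.** The plan gives no share of flagged people who have already refilled. The nearest figure is the power statement: 50% suppression in controls, a difference of .28, 100 per arm, power above 80%. With a two-sided alpha of 0.05 (not stated, so assumed) and the pooled two-proportion formula, power is 98.8%, so that statement is true. The smallest difference detectable with 80% power at 100 per arm is 19.3 points. The 350 per arm and the 70% power in the same paragraph do not follow from .28; that is a separate matter, and nothing here depends on it.

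**Reinitiation (secondary outcome).** Let f be the share of controls who would have failed the check, and p the reinitiation rate in the other controls. If all of the first group count as reinitiating, the observed control rate is (1 − f)p + f, so the overstatement is f(1 − p). Both f and p are assumptions.

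| f | p = 50% | p = 30% |
|---|---|---|
| 5% | 0.05 × 0.50 = 2.5 points | 0.05 × 0.70 = 3.5 points |
| 10% | 5 points | 7 points |
| 20% | 10 points | 14 points |

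**Viral suppression (primary outcome).** Let s be the suppression rate in controls who had already refilled, also assumed, and keep the plan's 50% for the rest. The control rate rises by f(s − 0.50). With 78% in the Program arm:

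| f | s | Rise in control rate | Observed difference | Power, 100 per arm | Power, 70 per arm |
|---|---|---|---|---|---|
| 5% | 65% | 0.05 × 0.15 = 0.0075 | 0.273 | 98.4% | 92.9% |
| 10% | 78% | 0.10 × 0.28 = 0.028 | 0.252 | 96.8% | 88.8% |
| 20% | 78% | 0.20 × 0.28 = 0.056 | 0.224 | 92.6% | 81.0% |
| 20% | 90% | 0.20 × 0.40 = 0.080 | 0.200 | 86.4% | 72.2% |

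The 70 per arm is 100 less the plan's 30% missing viral loads. Over the same range of f, the shift is 0.75 to 8 points, smaller than for reinitiation. With no true effect, the apparent difference would be the same size, against the program.

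**The case against.** The strongest reply is that both arms pass the same data-based screen and that a control must be confirmed late on the index date. A reader might infer that the control arm does contain people who had already refilled. The documents do not say so and give no count; *may contain* is all they support.

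A second reply is that a fill after the control's index date is a genuine usual-care outcome and not a misclassification. That is correct for the control alone. It does not restore comparability, because Program candidates with the same early fill were removed before enrollment.

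Third, the 10 business days under Phase 1 are not a measured claims lag at screening. They apply to the check after referral and cover the time to fill as well as reimbursement. This stands: the figure shows only that the plan expects some delay. Nor does the Outcomes section say that a fill dated before follow-up starts counts as reinitiation, so the f(1 − p) figures are an illustration in which every such control counts.

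Fourth, a reader might infer that the bias would hide the planned effect on the primary outcome. At .28 and 100 per arm it would not: power stays above 86% in every case shown. A smaller true effect would suffer more.

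Finally, a reader might infer that language is checked by phone, and so in one arm only. No section says that. The exclusion sits among the screening criteria, which apply to controls too. Its absence from the list of database items proves nothing, since other screening criteria, such as third-party insurance, are absent from it as well. What remains is an unstated data source.

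**Conclusion.** The point holds for refill status. As written, the last eligibility step is applied in one arm only, it selects on something close to an outcome, and the planned matching cannot repair it. The expected direction is against the program.

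The size cannot be derived from the documents. Under the assumed 5% to 20% of controls already refilled, all counted as reinitiating, control reinitiation is overstated by 2.5 to 14 points, against a detectable difference of about 19 points. For suppression the assumed range gives about 1 to 8 points. The defect deserves correction before analysis but does not by itself defeat the primary comparison at the planned difference. The language exclusion is a wording gap and not part of this conclusion.

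**What to change.** In the SAP, define analysis eligibility in both arms from claims, which are held for everyone:

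1. Give each control an index date that corresponds to the matched participant's date, at the same time since confirmed lateness. If consent is used, the control's index date is the control's first confirmed-late date plus the participant's interval from confirmed lateness to consent.
2. Require no ART fill dated on or before the index date in either arm. Look this up after claims run-out and before control data are de-identified, since no code key will exist afterwards.
3. Start control follow-up and outcome counting at that index date, not at the first confirmed-late date. This is essential: if the old start were kept, controls would gain a period in which by construction they cannot have refilled, and the bias would turn in the program's favor.
4. Reconcile this date with the Program start dates in Table 1, and state the order of matching and eligibility checks.
5. Report how many Program candidates were dropped at contact because they had already refilled. This gives the only direct evidence on f, and matters because fills outside Medicaid claims would stay invisible in controls.

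Separately, name the data source for the language exclusion.

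The cost is SAP wording and a repeat query of claims already held. The downside is a somewhat smaller control pool, possibly a few Program participants excluded if late-arriving claims show an earlier fill, and a short delay before controls are fixed.
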